10.3.2 Serious Adverse Events

The occurrence of an SAE must be immediately reported to Vifor Pharma (or its delegate; e.g., CRO) within 24 hours of awareness. This includes all SAEs (independent of relationship to study treatment) occurring from the time the informed consent is signed until 30 days following the last study visit or until 30 days after last study drug administration, whichever is longer. The final follow-up may be conducted as a telephone call rather than a formal visit, but the Investigator must report any SAEs that occur during this period. SAEs starting before first administration of study treatment must be identified as such.

A death occurring during the study or which comes to the attention of the Investigator within 30 days after the last study visit or until 30 days after the last study treatment administration, whichever is longer, whether considered treatment-related or not, must be reported to the CRO/Vifor Pharma.

SAEs must be reported by entering the SAE information into the eCRF. CRO (Worldwide Clinical Trial Pharmacovigilance department) will receive notification of the initial SAE via an email alert generated from the electronic data capture system.

The electronic SAE form will be completed with the following information at a minimum:

- Event description/verbatim (including onset date of the SAE, outcome and reason for it being considered serious)
- Relationship to investigational product (i.e., causality)
- Name of the investigational product (including study treatment dose and administration dates)
- Action taken with the investigational product
- Severity of the event

Additional information must be uploaded to the eCRF when available including any relevant records (e.g., hospital discharge summary, autopsy report/death certificate, etc.). Any supporting information provided should not reveal a subject's identity beyond the agreed study identifier. The Investigator should ensure that information reported is accurate and consistent.

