4.2.14. Time on Study

Time on study for safety purposes is calculated for each subject from SD1 to the last known date:

$$\text{Time on study (days)} = (\text{Last Known Date} - \text{SD1}) + 1.$$

Time on study for efficacy purposes is calculated for each subject from randomisation date to the last known date:

$$\text{Time on study (days)} = (\text{Last Known Date} - \text{Randomisation Date}) + 1.$$

If last known date is outside of visit window for Week 52 visit (i.e. after study day 375), time on study will be 375 days for such subjects and only events up to this day will be considered.

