4.2.18. Subject-Years of Time on Study

Subject-years of time on study is the sum of all subjects' times on study (overall or by treatment groups) expressed in years.

Subject-years of time on study = [Sum_i(time on study in days)] / 365.25, i=1 to n, where n is the number of subjects.

Note: for 30-days analysis, the time on study will be up to 30 days after randomisation.

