For the analysis of events within 30 days after randomisation, only events starting within these 30 days will be taken into account. Subjects with no event at 30 days will be censored at 30 days or last known date, whichever comes first. For the analysis of events up to 52 weeks, the first incidence of the relevant event up to the last known date or study day 375, whichever occurs first, will be taken into account. Subjects with no event will be censored at last known date or study day 375, whichever occurs first. In addition, a sensitivity analysis will be performed looking at events up to last available value (see section 4.2.16).

The probability of subjects having an event will be displayed by treatment group in the form of cumulative probability curves estimated using the non-parametric Kaplan-Meier method. Point estimates and corresponding 2-sided 95% CIs using the Greenwood's variance estimator will be provided at each scheduled visit (i.e., Weeks 6, 12, 24, and 52). Percentiles (25th, 50th, and 75th) and corresponding 2-sided 95% CIs will also be provided; any of the percentiles not reached will be presented as N/A. Survival estimates at each time point where any patient had event or was censored will be also displayed.

The number of subjects with at least 1 event and the event hazard rate per 100 subject-years “at risk” (estimated as the number of subjects with at least 1 event divided by the subject-years at risk of event) will be displayed by treatment group. Subject-years at risk of event will be taken as the sum of the observation time from start of study drug until the first occurrence of the event concerned, or until censoring. The hazard ratio (relative to placebo), its 95% CI and the associated p-value will be provided using Cox proportional hazards regression.

SAS code for time to event Cox regression (code may be updated to fit the data)

Assume the response variable, time to first event, is TFE and the censored status variable is EVENT (0=censored observation; 1=event observation).

The option 'rl' in the model statement produces 95% CI for the hazard ratio.

```
PROC PHREG DATA=dataset ;  
    CLASS armcd(ref='Placebo') sex hf_aetio hf_duration country /param=glm;  
    MODEL tfe*event_0= armcd sex age hf_aetio hf_duration country  
        / risklimits type3;  
    contrast "IV FCM. vs Placebo" armcd 1 -1 /estimate=exp;  
    ods output parameterestimates=parmest;  
        ods output ContrastEstimate=ContrastEstimate;  
RUN;
```

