- TEAEs by relationship to study drug.
- TEAEs by severity.
- Serious TEAEs.
- Related Serious TEAEs.
- Severe Serious TEAEs.
- TEAEs leading to treatment discontinuation.
- TEAEs leading to study discontinuation.
- All Fatal AEs.
- Fatal TEAEs.
- Related Fatal TEAEs.
- TEAEs leading to hospitalisation.
- TEAEs of clinical interest “CV Death” or “HF Hospitalisation”.
- TEAEs of special interest related to study drug.

Additionally, AEs in the categories listed below will also be summarised by incidence rates and adjusted incidence rates by SOC and PT, as well as number of events (Note: in the descriptive analysis for the incidence rate, each subject will contribute only once to the count for a given SOC or Preferred Term, regardless of the number of episodes experienced):

- TEAEs.
- TEAEs related to study drug.
- TEAEs by relationship (without adjusted incidence rates).
- Severe TEAEs.
- TEAEs by severity (without adjusted incidence rates).
- Serious TEAEs.
- Serious TEAEs occurring in > 5 % of the subjects.
- Non-serious TEAEs.
- Serious TEAEs related to study drug.
- TEAEs leading to treatment discontinuation, “drug withdrawn” in the eCRF.
- TEAEs leading to study discontinuation.
- Serious TEAEs by severity,
- Fatal TEAEs,
- Fatal TEAEs related to study drug,
- TEAEs of clinical interest (by PT only),
- TEAEs of special interest (by PT only) related to study drug.

Adjusted incidence rate will be calculated by dividing the number of subjects with a particular TEAE by the subject-years of time on study (see section 4.2.14) of all subjects in each treatment group.

In the tabulations by severity or relationship, each subject will contribute only once to each of the incidence rates by using the worst severity/strongest relationship reported within the period of interest; all events experienced will be counted in the event rates.

If the relationship is missing, the AE will be considered related to study drug. If the severity is missing, the AE will be considered to be severe.

Cardiovascular AE terms of clinical interest as reported by Investigators will be listed in this order in the table:

1. CV death
2. HF hospitalisation

The CV AEs of clinical interest as reported by Investigators will be identified as follows:

1. For HF hospitalisations: PT = “Cardiac failure”, “Cardiac failure acute”, “Cardiac failure congestive”. or “Cardiac failure chronic” and led to or prolonged hospitalisation = Yes

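### The adjusted adverse event rate leaves time after a subject's first event in its denominator; under a constant hazard over one year, first-event rates come out about 5% low at 10% incidence, 15% at 29% and 28% at 50%

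*SAP*

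**What the plan says.** SAP 4.8.2 sets the adjusted incidence rate for the tables by system organ class and preferred term: "Adjusted incidence rate will be calculated by dividing the number of subjects with a particular TEAE by the subject-years of time on study" "of all subjects in each treatment group". For the incidence count, "each subject will contribute only once to the count for a given SOC or Preferred Term", however many episodes occur.

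The denominator is built in two other sections. SAP 4.2.14: "Time on study for safety purposes is calculated for each subject from SD1 to the last known date". SAP 4.2.18: "Subject-years of time on study is the sum of all subjects' times on study". Neither stops the time at an adverse event.

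For time-to-first-event endpoints, SAP 4.6.2 instead uses subject-years at risk, which run from the start of study drug "until the first occurrence of the event concerned, or until censoring".

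On the end of follow-up, SAP 4.2.14 caps time on study at 375 days when the last known date is later, and adds that "only events up to this day will be considered". Protocol 10.3.2 collects serious adverse events from consent "until 30 days following the last study visit", or until 30 days after the last dose if that is longer.

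**The concern.** Once a subject has had a first event of a given term, that subject cannot add to the numerator again but goes on adding to the denominator. The quotient is therefore lower than the rate of first events among subjects still at risk, and the gap widens as the event becomes more frequent.

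Two things are at stake. First, the same outcome can appear in one report on two scales. Heart failure hospitalisation is an efficacy outcome with an at-risk rate and also an investigator-reported event of clinical interest with a total-follow-up rate. A reader could not separate the denominator difference from the difference between adjudicated and investigator-reported events. Second, if onset patterns are similar, the arm with more affected subjects has its rate lowered more, which moves rate contrasts towards no difference.

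**Working it through.** The documents give no expected adverse event rate for this trial and no size for this effect, so there is no figure of the plan's own to reproduce.

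**General result.** Let D be the number of subjects with the event, Y the total subject-years and R the subject-years up to the first event. The planned rate is D/Y and the at-risk rate is D/R. The understatement is 1 − (D/Y)/(D/R) = 1 − R/Y, the share of all follow-up that falls after the first event. If subjects with and without the event have similar follow-up, this share cannot exceed p, the proportion affected.

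**Constant hazard over one year.** The planned rate is p per subject-year and the at-risk rate is −ln(1−p), so the understatement is 1 − p/[−ln(1−p)].

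Inputs for p from the documents:
- 10%: upper end of the range for the most common adverse drug reactions (Protocol 8.2).
- 17%: treatment-related events in earlier studies (Protocol 1.2).
- 29%: subjects with at least one heart failure hospitalisation. SAP 4.1 assumes 35% with that or CV death, and that half of the 12% with CV death have no prior such hospitalisation, so 35 − 6 = 29.
- 50%: any treatment-emergent event in earlier studies (Protocol 1.2).

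Rates per 100 subject-years:

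| p | As planned | At risk | Understated by | Same, with 12% deaths |
|---|---|---|---|---|
| 10% | 10.0 | 10.5 | 5.1% | 5.3% |
| 17% | 17.0 | 18.6 | 8.8% | 9.1% |
| 29% | 29.0 | 34.2 | 15.3% | 16.0% |
| 50% | 50.0 | 69.3 | 27.9% | 29.1% |

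For example, at 50%: −ln(0.5) = 0.693 and 1 − 0.500/0.693 = 0.279. The last column adds an independent death hazard giving the 12% death rate in the protocol synopsis. A quarter is reached at p = 45.4%, or 43.7% with deaths.

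**Early onset.** If events occur on average t weeks after the start, the understatement is p(1 − t/52). Protocol 1.2 puts the phosphorus nadir about 2 weeks after dosing. With every onset at 2 weeks, 10% incidence gives 0.10 × 50/52 = 9.6% and 29% gives 27.9%; a quarter is reached at about 26%. With mean onset at 12 weeks, a quarter is reached at about 32.5%.

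**Fatal events.** Follow-up ends at the event, so R is close to Y and the effect is essentially nil. Events that end study participation leave little time afterwards.

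**Contrasts between arms** (illustrative proportions, constant hazard):
- 50% v 40%: planned ratio 0.50/0.40 = 1.25; at-risk ratio 0.693/0.511 = 1.36.
- 10% v 5%: planned ratio 2.00; at-risk ratio 0.1054/0.0513 = 2.05.

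**The day-375 sentence.** It directly follows the efficacy formula in SAP 4.2.14, but that section also covers safety, and SAP 4.8.2 refers back to it. With a Week 52 visit on target day 365, serious events are collected to about day 365 + 30 = 395. The wording leaves open whether events from day 376 to day 395 enter the tables and, if so, over which denominator.

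**The case against.** The strongest reply is that little depends on this column. Protocol 12.8 makes the safety analysis descriptive, and the subject percentages and numbers of events are reported beside the adjusted rate. With equal follow-up in the two arms, the planned ratio is simply the ratio of those percentages, a legitimate risk ratio; the at-risk ratio is a different measure. The definition is stated openly, and the constant hazard is doubtful when doses are given only at Weeks 0, 6, 12 and 24. All of this stands. It limits the importance of the point but does not make the quotient a first-event rate.

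A reader might infer that common event rates are understated by a quarter or more. The documents do not support that in general: under a constant hazard it needs about 45% of subjects affected. An any-event row could reach that level, but SAP 4.8.2 specifies its overview table as numbers and percentages and attaches the adjusted rates to tables by class and term, where few single terms are likely to be so frequent. Nor would a safety signal be hidden: at 10% v 5% the ratio hardly moves, and the percentages remain visible.

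A reader might also infer that late serious events and deaths drop out of the report. The documents do not show this. Outside SAP 4.2.14, day 375 appears only in efficacy text. The definition of a treatment-emergent event in SAP 4.8.2 has no end date, and that section lists serious adverse events and the details of all deaths. Routine adverse event reporting ends at the Week 52 visit in any case (Protocol 10.3.1). What remains is an ambiguity of wording.

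**Conclusion.** The point holds as a matter of definition and is small for most terms. The planned quotient mixes a first-event numerator with a total-follow-up denominator and departs from the SAP's own at-risk convention. For the most common adverse drug reactions the understatement is about 5% or less under a constant hazard, and under 10% even with very early onset. It becomes material only for very frequent categories or for frequent events with early onset. The shrinkage of contrasts between arms is modest and is measured against at-risk rates.

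The sizes rest on three assumptions that the documents do not state: a constant hazard over one year (except in the early-onset variant), similar follow-up in subjects with and without the event, and similar onset patterns in the two arms. The arm contrasts use illustrative proportions. The change is worth making because it is cheap, but no conclusion of the trial depends on it.

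**What to change.** In SAP 4.8.2, define the adjusted incidence rate as the number of subjects with the event divided by subject-years at risk. Run each subject's time from first dose to the first event of that category, or to the end of safety follow-up if there is none, and define that end date. If the present denominator is kept, label the measure as subjects with an event per 100 subject-years of total follow-up, so that it is not read as a first-event rate.

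In SAP 4.2.14, state that the day-375 cut applies to efficacy, and say how serious events collected after the last visit are handled, with the same cut-off in numerator and denominator.

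The cost is a few lines of SAP text and a term-specific denominator in the adverse event program. No new data are needed.

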Since the developmental international birth date, more than 7,000 subjects are known to have been exposed to FCM with at least one dose in more than 35 completed prospective, interventional clinical studies. Across various clinical studies, replenishment of iron stores has been consistently observed. Markers of ID have included both TSAT and serum ferritin. In subjects with more severe or prolonged ID that has led to anaemia, correction of ID using FCM has consistently resulted in medically significant increases in haemoglobin (Hb) values (correction of anaemia). This improvement was usually seen within 2 weeks. In addition to the correction of laboratory parameters, iron replacement therapy has demonstrated significant improvements in subject QoL and functional status. Ferric carboxymaltose was well tolerated by study participants. In the completed clinical studies, up until the 1 January 2015, approximately 50% of the subjects experienced at least 1 treatment-emergent adverse event (AE), and events considered related to treatment occurred in just over 17% of subjects who received FCM. The most commonly reported adverse drug reactions (ADRs) in the FCM group were nausea, injection/infusion site reactions, hypophosphataemia, headache, flushing, dizziness, and hypertension.

In relation to laboratory parameters recorded in clinical studies, no consistent pattern of clinically meaningful changes requiring intervention have been observed. However, mild and transient changes of liver enzymes, such as aspartate aminotransferase and alanine aminotransferase, gamma-glutamyl transferase and alkaline phosphatase, have been reported in some studies. A transient decrease in blood phosphorus levels was frequently observed. The nadir occurred approximately 2 weeks after dosing and resolved without treatment in most subjects within the follow-up period of up to 12 weeks. Severe hypophosphataemia (i.e., <0.3 mmol/L) was observed in very few cases, and was of short duration.

No formal interaction studies have been performed. Except for the reduced uptake of oral iron administered in parallel with parenteral iron, no interactions with other medications are known.

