9.2.3.11 Laboratory Tests Mandated by the Study Protocol

The laboratory tests mandated by the trial protocol to be transferred into the eCRF will be analysed locally. The assays to be performed are Hb, serum ferritin, TSAT, serum phosphorus and serum pregnancy tests in females of childbearing potential.

If available in the subject clinical records within the Index hospitalisation, the latest serum creatinine value measured before randomisation visit will be collected.

Iron status blood test reports and serum phosphorus levels received after randomisation must be provided directly to the unblinded Investigator. This person must enter the results in the eCRF page provided for this purpose.

In addition, blood samples for biomarkers will be taken in a subset of subjects. The baseline biomarker blood sample will be drawn just prior to the injection of study treatment. Blood samples will be stored for up to three years after the end of the trial for future analyses of biomarkers of scientific interest. Details concerning the blood samples storage will be provided in an instruction manual and results of these exploratory analyses will be not part of the clinical study report of the main study.

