2.5.4. Safety Endpoints

- Incidence of adverse events (AEs): by System Organ Class (SOC) and Preferred Term (PT) (Medical Dictionary for Regulatory Activities (MedDRA) coded term), by maximum severity, related to study drug, leading to study drug discontinuation, serious, leading to death, and adjudicated.
- Incidence of AEs of clinical interest: HF hospitalisation and CV death.
- Incidence of Special Situation Events.
- Incidence of event adjudication (Hospitalisation, Urgent HF visit and Deaths).
- Incidence of related AEs of special interest: Hypersensitivity reactions, Hypophosphatemia, Injection/infusion site reactions and Haemosiderosis.
- Clinical laboratory panels (absolute and change from baseline, incidence of laboratory abnormalities).
- Vital Signs (absolute and change from baseline).
- Electrocardiograms (incidence of electrocardiogram abnormalities, QTc measurement meeting ICH E14 criteria [2]).
- Prior, concomitant and newly started medications.

Note: biomarkers exploratory analyses will not be part of the CSR of the main study. They will be described in a separate biomarker SAP.

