2. For CV death: SOC = “Cardiac Disorders” and results in death = Yes, and PT=”Sudden cardiac death” in SOC “General disorders and administration site conditions”

AEs of special interest include “hypersensitivity reactions”, “hypophosphatemia”, “injection/infusion site reactions” and “haemosiderosis”. Only events related to study drug are considered. Each category will be identified as follows:

1. Hypersensitivity reactions: PT = “Hypersensitivity”, “Anaphylactic reaction”, “Anaphylactic shock”, “Anaphylactoid shock” or “Anaphylactoid reaction”
2. Hypophosphatemia: PT = “Blood phosphorus decreased”, “Blood phosphorus abnormal”, “Hypophosphataemia”, “Hypophosphataemic osteomalacia” or “Hereditary hypophosphataemic rickets”
3. Injection/infusion site reactions: HLT = “Infusion site reaction”, “Injection site reactions”, “Administration site reactions NEC” or “Infusion related reaction”
4. Haemosiderosis: PT = “Haemosiderosis”, “Haemeatochromatosis”, “Iron overload”, “Hepatic siderosis”, “Cardiac iron overload”, “Pulmonary haemosiderosis” or “Superficial siderosis of central nervous system”

A listing of pre-study AEs and listing of AEs starting between randomisation date and start of treatment will be presented. All TEAEs occurring on study will be listed in subject data listings, as will related TEAEs, SAEs, related SAES, TEAEs leading to study drug discontinuation or death. Data will not be imputed in the listings.

Relevant pregnancy information captured in the eCRF will be listed.

All deaths details will be listed.

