		14.3.1.13 Serious TEAEs by System Organ Class, Preferred Term, Severity and Treatment Group – Safety Analysis Set
		14.3.1.14 Fatal TEAEs by System Organ Class, Preferred Term and Treatment Group – Safety Analysis Set
		14.3.1.15 Fatal TEAEs Related to Study Product by System Organ Class, Preferred Term and Treatment Group – Safety Analysis Set

Type*	Section	Title
		14.3.1.16 TEAEs of Clinical Interest by Event Type, Preferred Term and Treatment Group – Safety Analysis Set
		14.3.1.17 TEAEs of Special Interest Related to Study Product by Event Type, Preferred Term and Treatment Group – Safety Analysis Set
L	14.3.2 AE Listings	14.3.2.1 TEAEs Related to Study Product – Safety Analysis Set

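### Adverse events of special interest are compared between arms only when judged drug-related, and no all-causality count per category is planned

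*SAP*

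**What the plan says.** The relatedness condition is applied wherever the SAP summarises events of special interest:

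- SAP 2.5.4, the endpoint: "Incidence of related AEs of special interest: Hypersensitivity reactions, Hypophosphatemia, Injection/infusion site reactions and Haemosiderosis".
- SAP 4.8.2, the definition of the categories: "Only events related to study drug are considered".
- SAP 4.8.2, the summaries: "TEAEs of special interest (by PT only) related to study drug". The corresponding line of the adverse event overview has the same limit.
- SAP 7.1, Table 14.3.1.17: "TEAEs of Special Interest Related to Study Product by Event Type, Preferred Term and Treatment Group". No other table of special-interest events is listed.

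Three categories are defined by lists of preferred terms. The injection or infusion site category is defined by high level terms.

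On who sees what, Protocol 9.2.3.11 says that iron and phosphorus reports after randomisation "must be provided directly to the unblinded Investigator". Protocol 6.2 makes the unblinded physician responsible for evaluating the iron values and sends that physician to Section 10.2.6, under which the Investigator decides whether a laboratory change counts as an adverse event. Protocol 10.2.2 gives the causality judgement to a medically qualified Investigator and is silent on blinding. SAP 2.2 says that unblinded staff take no other part in efficacy or safety assessments and that the blinded team does the follow-up assessments.

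**The concern.** Randomisation already supplies the causal comparison: if the drug causes hypophosphataemia, more of it will be seen on FCM. Counting only events that someone attributes to the drug puts an opinion in place of that comparison. If attribution is equally strict in both arms, events are lost but the ratio is preserved. If attribution differs by arm, the ratio is distorted. Calling placebo events unrelated exaggerates an excess on FCM, and putting FCM events down to heart failure or other illness hides one.

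The risk is most concrete for hypophosphataemia and haemosiderosis, because a person who knows the arm receives the laboratory results from which such events would be recognised. The other two categories are clinical events, and the laboratory route does not apply to them.

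The filter is also not the SAP's general practice. In the same section, the events of clinical interest (CV death and HF hospitalisation) are counted with no relatedness condition.

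**Working it through.** The plan states no incidence or attribution rate for these events, so there is no figure to reproduce. The check is mainly a reading of the documents against each other.

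**Step 1. Is the by-category count available anywhere without the filter?**

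- Table 14.3.1.2 gives all TEAEs by system organ class, preferred term and arm, and Table 14.3.1.4 splits them by relationship. Both are unfiltered, but neither groups terms into the four categories.
- SAP 4.8.2 counts a subject once per preferred term. A subject with two terms from one category appears in two rows, so adding rows does not give subjects per category.
- The injection or infusion site category is built on high level terms. The tables stop at organ class and preferred term, so this group is not shown unfiltered and cannot be rebuilt from them.
- Listing 16.2.7.5 covers hypersensitivity reactions, but it is a listing and not a summary by arm.
- SAP 4.8.5 plans by-arm summaries of phosphorus, ferritin and TSAT, with a phosphorus shift table to the lowest post-baseline value. These depend on no causality opinion, but they show measurements and not events.

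The answer is no: the all-causality subject count per category is missing.

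**Step 2. Could the causality opinion depend on the arm?**

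- Protocol 9.2.3.11 and 6.2 put the post-randomisation results in unblinded hands and link the unblinded physician to the rule for calling a laboratory change an adverse event.
- Protocol 4.1.2 and 6.2 exempt the interpretation of these results from the bar on unblinded staff taking part in assessments. SAP 2.2 has no such exemption.
- Protocol 10.2.2 does not say whether the person assigning causality is blinded.

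These statements are in tension and leave the possibility open. They do not show that unblinded attribution happens.

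**Step 3. What would unequal attribution do?** This is illustration only. The inputs are 550 per arm (SAP 2.2) and a true incidence *p* that is equal in both arms, taken as 1% to 10%. That range is borrowed from the frequencies of common reactions in Protocol 8.2 and is an assumption here. The attribution rates *q* are invented.

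Counted events per arm = 550 × *p* × *q*.

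| *p* | All events per arm | FCM, *q* = 0.9 | Placebo, *q* = 0.5 | Ratio |
|---|---|---|---|---|
| 1% | 5.5 | 5.0 | 2.8 | 1.8 |
| 5% | 27.5 | 24.8 | 13.8 | 1.8 |
| 10% | 55.0 | 49.5 | 27.5 | 1.8 |

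- With 0.7 against 0.5, the ratio is 0.7 / 0.5 = 1.4.
- With 0.5 in both arms, the ratio is 1.0 and half the events are lost.
- With the rates reversed (0.5 on FCM, 0.9 on placebo), a true doubling from 5% to 10% would show 550 × 0.10 × 0.5 = 27.5 against 550 × 0.05 × 0.9 = 24.75, a ratio of 1.11.

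Without the filter, equal incidence gives equal expected counts whatever *q* is.

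**The case against.** The best defence is that little is hidden. All preferred terms are tabulated by arm regardless of relationship and again split by relationship. Measured phosphorus, ferritin and TSAT are summarised by arm. Safety is descriptive throughout (Protocol 12.8). The attribution rules also lean towards inclusion: possible counts as related, and SAP 4.8.2 treats a missing relationship as related. All of this is correct. It rules out saying that the unfiltered comparison is never shown, and it limits what is lost to the grouped count per category. It does not defend the filter, because the inclusive rules guard against missing data and not against judgement that differs by arm.

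A second objection also stands. An all-causality row does not remove every dependence on the arm. Under Protocol 10.2.6, whether a laboratory change is reported as an adverse event at all is itself a judgement, and the unblinded physician is directed to that section. For the two laboratory-based categories, only the measured values are free of this.

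A reader might infer that causality for these two categories *is* judged unblinded. The documents do not say so. They leave the role undefined, and SAP 2.2 points the other way.

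A reader might also take the programme figures in Protocol 1.2 as a measure of the filter: approximately 50% of subjects had any treatment-emergent event, and "events considered related to treatment occurred in just over 17% of subjects who received FCM". The quotient, 17 / 50 = 34%, would suggest that about two thirds of subjects with events drop out. That does not transfer. The figures cover all event types in other studies, one subject can have both related and unrelated events, and these categories were singled out as being of special interest for this drug.

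**Conclusion.** The point holds in a limited form. As planned, the comparison of special-interest events by category and arm depends on a causality opinion. For hypophosphataemia and haemosiderosis the documents do not protect that opinion from knowledge of the arm. No planned table gives subjects per category regardless of causality, and the injection or infusion site group is not shown unfiltered as a group.

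The size and direction of any bias cannot be computed from the documents. The ratios of 1.8, 1.4 and 1.11 above rest wholly on assumed attribution rates and show only that such a filter can create or mask a difference. It would also go too far to call this the trial's key safety comparison: it is one of several descriptive safety endpoints in the SAP.

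**What to change.** - In SAP 2.5.4, 4.8.2 and Table 14.3.1.17, present each category by arm for all TEAEs regardless of causality as the main result, counting each subject once per category. Keep the related subset as a supplementary row.
- State that hypophosphataemia and haemosiderosis are to be read beside the measured phosphorus, ferritin and TSAT tables of SAP 4.8.5, because event reporting itself may depend on the arm.
- State who judged adverse event status and causality for laboratory-based events, and whether that person was blinded, and reconcile SAP 2.2 with Protocol 6.2 and 9.2.3.11.
- As a minor correction, check the listed term "Haemeatochromatosis" against the MedDRA preferred term. Protocol exclusion criterion 10 uses a different spelling (haemochromatosis), and an exact string match on the listed form would miss it. The SAP does not say that matching is literal, so this may have no effect.

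The cost is a few extra table rows and some clarifying text. All the data are already collected.
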